#### 10.4 Conjunctival Impression Cytology

Impression cytology of the bulbar conjunctiva is a procedure in which the quantity and quality of epithelial cells and component of the ocular surface are evaluated; the primary focus is to evaluate the density and amount of goblet cells in the sample. The observation will take place in the single and specialized center of pathology under digital counting and it will be confirmed by observation.

The procedure consists of the following steps:

1. Tetracaine instillation over the ocular surface
2. Eye speculum placing
3. A minicell will be taken with the mounted Millipore paper.
4. This will be placed manually in contact with the Millipore surface over the nasal bulbar conjunctiva, slightly pressing, without indenting the surface.
5. Cytological fixation spray will be applied (96% alcohol cytospray)
6. This will be placed on a clean and dry bottle to transport it to the sample gathering unit

### 10.5 *Posterior Segment Examination:*

A review of the posterior segment shall be performed to verify that there is no pathological process that requires attention and/or prevents the entry of the subject to the trial.

The posterior segment will be explored under drug induced mydriasis, as well as the rest of the retina, checking the following details:

1. Vitreous humor appearance
2. Totally attached retina
3. Vascular alterations
4. Clinical macular area appearance
5. Foveolar area appearance
6. Optical nerve characteristics
  - a. Vessel emergency
  - b. Neuro-retinal ring
  - c. Relation with the whole disc area and cup excavation will be expressed in decimals
7. Report any other clinical finding on the retina.

## 11. Procedures to Perform per Visit

---

### 11.1 *Baseline visit:*

1. During the visit, first the informed consent will be checked, clarifying all doubts that the subject wants to review, and recording in the case report format (CRF) the possible questions and the answers given to the subject; this procedure will be carried out strictly by the health staff, preferably by principal investigator.
2. Then, the signing of the informed consent, together with the two witnesses (if applicable) will be done.
3. Eligibility and exclusion criteria will be evaluated.
4. Pregnancy test will be performed (if it applies).
5. The medical staff will provide a patient with a medical history , emphasizing the signs and symptoms related with the systemic inflammatory diseases.
6. A complete ophthalmic clinical history, covering at least the points required on the CRF plus the points required by medical history first used on the research center will be made.
7. An evaluation about all the concomitant drugs will be done.
8. An OSDI questionnaire will be given.
9. A subject number will be given.
10. Ophthalmic examination:
  - a. Visual acuity and best-corrected visual acuity
  - b. Biomicroscopy
  - c. Rose Bengal staining on the ocular surface
  - d. Fluorescein staining on the ocular surface
  - e. Intraocular pressure measuring with Goldman tonometer
  - f. Schirmer Test

- g. Drug induced mydriasis with tropicamide/phenylephrine. Fundoscopy on a slit lamp with a 90D or 78D fundus lens.
- h. Drug product delivery
- i. Impression cytology

11. Delivery of the assigned medication to the subject.

12. Schedule the following visits.

### 11.2 Visit 1 (day 7)

- 1. Medical and ophthalmologic clinical history.
- 2. Ophthalmic Examination:
  - a) Visual acuity and best-corrected visual acuity
  - b) Schirmer test type 2 (after tetracaine instillation 5mg/ml)
  - c) Biomicroscopy (evaluate chemosis, conjunctival hyperemia, iris and crystalline appearance).
  - d) OSDI questionnaire
  - e) Rose Bengal staining on the ocular surface
  - f) Fluorescein staining on the ocular surface
  - g) Tear film breakup time. TBUT
  - h) Intraocular pressure measuring with Goldman tonometer
  - i) Review of attachment to medication.
- 3. Subject's journal checking and adherence to the study
- 4. Adverse events review or concomitant drug product modification
- 5. Schedule the following visit
- 6.

### 11.3 Visit 2 (day 30)

1. Ophthalmic Examination:
  - a) Visual acuity and best-corrected visual acuity measuring
  - b) Biomicroscopy
  - c) OSDI questionnaire
  - d) Rose Bengal staining on the ocular surface
  - e) Fluorescein staining on the ocular surface
  - f) Tear film breakup time.TBUT
  - g) Intraocular pressure measuring with Goldman tonometer
  - h) Review of attachment to medication.
2. Subject's journal review and adherence to the study
3. Adverse events review or concomitant drug product modification
4. Schedule next visit.

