### 5.2 *SPECIFIC OBJECTIVES:*

**5.2.1** To evaluate the safety of the preservative-free ophthalmic formulation PRO-087 (by Laboratorios Sophia, S.A. de C.V.) on the corneal and conjunctival epithelium, intraocular pressure, and structures of anterior and posterior segment in patients with tear film dysfunction syndrome from mild to moderate.

**5.2.2** To determine the correlation between improvement of clinical status and perceived improvement of symptoms of each participant in each study group.

**5.2.3** To compare the qualitative and quantitative histological status of the ocular surface before and after the pharmacological intervention in each study group to determine the evolution under the intervention of PRO-087.

**5.2.4** To evaluate the quantitative rating of tear film production by the Schirmer Test throughout the study.

**5.2.5** To qualitatively assess the tear film production by measuring the tear film break-up time stained with fluorescein and cobalt filter.

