## 9. Study Schedule

FOLLOW UP						
Procedure	Baseline visit	Visit 1	Visit 2	Visit 3	Final visit	Follow-up call
	Day 1	Day 7	Day 30	Day 60	Day 90	Day 105
Eligibility criteria (inclusion and exclusion)	X					
Pregnancy test (if applicable)	X				X	
Informed consent sign	X					
Medical and ophthalmic history (A,B,C).	X	X	X	X	X	
OSDI questionnaire	X	X	X	X	X	
Code assignment to the subject	X					
Visual acuity and Best-corrected visual acuity	X	X	X	X	X	
Conjunctival impression cytology	X				X	
Fluorescein staining	X	X	X	X	X	
Tear break-up time	X	X	X	X	X	
Rose Bengal staining	X	X	X	X	X	
Schirmer Test	X	X	X	X	X	
Anterior biomicroscopy (D, E, F, G, L)	X	X	X	X	X	
Posterior ophthalmoscopy under mydriasis (H, I, J, K)	X				X	
IOP measurement	X				X	
Treatment delivery	X					
Subject journal review	X	X	X	X	X	
Adverse events evaluation		X	X	X	X	
Drug product application	X	X	X	X	X	
Drug product devolution					X	
Concomitant drug product evaluation	X	X	X	X	X	
Safety phone call						X

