#### *10.3.6 Tear Drop Break-up Time*

[figure not shown]
It will be measured at the end of a blink and the patient will be asked not to blink immediately until the tear film on the cornea is broken, if it exceeds 10 " it is considered as normal.

Example:

[figure not shown]

10.3.7 Epithelial Defects on:

10.3.7.1 CORNEA: Epithelial defects will be analyzed by the approximate percentage of the total corneal area, with 100% as all the corneal area. Example:

[figure not shown]

10.3.8 CONJUNCTIVA: It will be qualitatively assessed, according to the extension of the conjunctiva fluorescein deposits, as shown below:

After the fluorescein staining described is done we will take the intraocular pressure (IOP) with a Goldman tonometer, the result will be reported in millimeters of mercury, this is performed only at baseline and final visits.

Once the above aspects are valued, integrate them into a single criterion according to the scale of the University of Oxford, based on this evidence, which proves to have more correlation with the score of the OSDI and Schirmer test.

Panel	Grade	Criterion
A 	0	Equal to or less than panel A

[figure not shown]
[figure not shown]

B		I	Equal to or less than panel B
C		II	Equal to or less than panel C, more than panel B
D		III	Equal to or less than panel D, more than panel C
E		IV	Equal to or less than panel E, more than panel D
> E		V	More than panel E

Fig. 10.3.8.1

10.3.9 Schirmer Test:

Schirmer test involves the quantitative measurement of the amount of tears produced in the eye for 5 minutes, and it is quantified millimetrically on filter paper strips validated for the test. The procedure will be standardized as follows:

1. After instillation of topical tetracaine is instilled over the ocular surface, filter paper strips are placed on the lower lid of the subjects and they will be asked to close their eyes for 5 minutes.
2. After 5 minutes the strips will be removed; the findings will be reported in millimeters.
3. Likewise, assessment will be made as follows:
  - a Normal: > 15 mm
  - b Mild: < 14 mm - > 9 mm
  - c Moderate: > 4 mm. < 80 mm

d      Serious: < 4 mm.

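### The day-30 visit list omits the scheduled Schirmer test, and the lists for days 7, 30 and 60 add intraocular pressure readings that the schedule and section 10.3 exclude

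*Combined protocol and SAP*

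**What the plan says.** **Schirmer test.** The section 9 schedule has the row "Schirmer Test X X X X X", which covers baseline and days 7, 30, 60 and 90. Specific objective 5.2.4 is "To evaluate the quantitative rating of tear film production by the Schirmer Test throughout the study". In section 11 the test is listed at baseline (11.1), day 7 (11.2), day 60 (11.4, Visit 3) and day 90 (11.4, Final visit). The list under "11.3 Visit 2 (day 30") runs from item a to item h and does not include it.

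**IOP.** The schedule row reads "IOP measurement X X", with the marks at baseline and the final visit. The procedure text after 10.3.8 says of IOP that "this is performed only at baseline and final visits". Yet the lists for days 7, 30 and 60 each carry "Intraocular pressure measuring with Goldman tonometer".

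**Use of the data.** Section 13.3 bases the total of 288 subjects on the Schirmer test. Section 15 assigns intra-group differences to a repeated-measures ANOVA and between-group differences to a separate ANOVA. Section 14.3.1 makes a Schirmer fall of more than 20%, and an IOP below 7 or above 21 mmHg, safety parameters. The text before that table sets the limit at 5% of subjects. Section 14.1 and the same safety text place the evaluation of their variables at the scheduled visits.

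**The concern.** Section 11 is the protocol's list of procedures for each visit. A site that works through it as written performs no Schirmer test at day 30 and takes three IOP readings that two other places exclude. A site that works from the schedule does the opposite. Both can claim to follow the protocol.

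A Schirmer value not taken at day 30 cannot be recovered. It is missing from the intra-group repeated-measures ANOVA, for which section 15 gives no missing-data method, and from the check for a fall of more than 20%. If some sites collect it and others do not, a classical complete-case repeated-measures ANOVA must drop either the visit or the affected subjects.

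For IOP, the safety rule counts subjects against a limit but does not say which reading counts. The chance that a subject is flagged depends on how many readings are eligible, so the result of the rule can depend on which list was followed.

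**Working it through.** **1. Visit-by-visit comparison**

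| Visit | Schirmer, section 9 | Schirmer, section 11 | IOP, section 9 and 10.3 | IOP, section 11 |
|---|---|---|---|---|
| Baseline | yes | yes | yes | yes |
| Day 7 | yes | yes | no | yes |
| Day 30 | yes | **no** | no | **yes** |
| Day 60 | yes | yes | no | yes |
| Day 90 | yes | yes | yes | yes |

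IOP also conflicts at days 7 and 60. The Schirmer test conflicts only at day 30. The day-7 and day-60 lists both carry it as item b, so its absence at day 30 looks like a drafting slip.

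**2. Volume of data, with 288 subjects and no losses**

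- Schirmer: 288 × 5 = 1,440 subject-visits under the schedule, against 288 × 4 = 1,152 under section 11. The difference is 288 subject-visits, or 1 of 4 post-baseline values (25%). This is a ceiling: it needs every site to follow 11.3.
- IOP: 288 × 2 = 576 subject-visits under the schedule, against 288 × 5 = 1,440 under section 11. The difference is 864. Post-baseline, that is one reading per subject against four.

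**3. Sample size**

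The later arithmetic in section 13.3 reproduces: 80 × 1.2 = 96 and 96 × 3 = 288. The 80 does not. With SD 1.72 and difference 0.13, 2 × [(1.96 + 0.84) × 1.72 / 0.13]² is about 2,745 per group. That is a separate problem. It does not alter the fact that the plan sizes the trial on the Schirmer test, and correcting the visit lists does not change the number of subjects.

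**4. IOP and the 5% limit**

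The documents give no rate of out-of-range readings. Assume a chance p = 2% per reading at subject level.

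- One post-baseline reading: 2.0% of subjects flagged.
- Any of four, independent: 1 − (1 − 0.02)⁴ = 7.8%.
- Any of four, perfectly correlated: 2.0%.

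Readings from one subject are correlated. With an equicorrelated normal model and one tail, P(any of four) = 1 − ∫ Φ((c − √ρ·u)/√(1 − ρ))⁴ φ(u) du, where Φ(c) = 0.98:

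| Correlation ρ | Flagged by any of four |
|---|---|
| 0 | 7.8% |
| 0.5 | 6.4% |
| 0.7 | 5.3% |
| 0.8 | 4.7% |
| 0.9 | 3.8% |

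At this assumed rate the expected share passes 5% at a correlation of 0.7 but not at 0.8.

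**The case against.** The best reply is that the protocol does indicate which part to follow. Section 14.1 and the safety text before 14.3.1 refer evaluation to the scheduled visits. Section 15 defines completers by the visits in the activity schedule. Objective 5.2.4 agrees with the schedule on the Schirmer test, and section 10.3 agrees with it on IOP. Only the section 11 lists differ. On this reading the extra IOP readings need not enter the safety count at all. This carries weight, and a reader should not infer that the documents are silent on precedence. It does not close the matter: the evaluation then expects a day-30 Schirmer value that the per-visit list never requests, and no sentence expressly places the schedule above section 11.

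The Schirmer loss is also a worst case. The documents do not say which section sites work from, and the case report forms are not available to check. Baseline and day-90 values are listed in both places. If every site skipped day 30, four common time points would remain and no subject need be dropped. All of this stands.

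On IOP, a reader might infer that the safety verdict flips for any per-reading rate from about 1.3% to 5%. That range holds only for independent readings: 1 − (1 − 0.013)⁴ = 5.1%. The safety rule also refers to both eyes without saying how they combine, and the calculation does not model this.

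A reader might also see the lack of a separate tear break-up time item in the baseline and final lists as a further omission. The documents do not support that. Section 9.1 places break-up time within biomicroscopy (item L), and sections 10.3.5 and 10.3.6 place it in the examination after fluorescein staining. Both examinations are on those lists.

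**Conclusion.** The contradiction is real and follows from the text alone. Section 11.3 omits a Schirmer test that the schedule requires, and sections 11.2, 11.3 and 11.4 (Visit 3) list IOP at three visits where the schedule and section 10.3 exclude it.

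For the Schirmer test, the cost at a site that follows 11.3 is the day-30 value, for both the intra-group analysis and the safety check. It would be too strong to say that the main comparison or the trial's size is compromised.

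For IOP, the number of eligible readings can move the flagged share across the 5% limit, but whether it does depends on quantities that the documents do not give. The 2.0% to 7.8% range rests on the assumed 2% rate, and the intermediate figures rest on the normal model as well. They show sensitivity and are not a forecast.

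This should be corrected because a missed day-30 value is unrecoverable and the correction is simple.

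**What to change.** 1. Add the Schirmer test to section 11.3, in line with the schedule and objective 5.2.4.
2. Reconcile the IOP timing across the section 9 schedule, the text after 10.3.8, and sections 11.2, 11.3 and 11.4 (Visit 3). The choice of visits is for the sponsor and investigators.
3. State in the safety criteria which IOP reading or readings enter the 5% count.

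The cost is a text correction to the protocol. The Schirmer change adds no procedure beyond those already in the schedule.

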### 11.4 Visit 3 (day 60)

1. Medical and ophthalmologic clinical history.
2. Ophthalmic Examination:
  - a) Visual acuity and best-corrected visual acuity
  - b) Schirmer test type 2 (after tetracaine instillation 5mg/ml)
  - c) Biomicroscopy (evaluate chemosis, conjunctival hyperemia, iris and crystalline appearance).
  - d) OSDI questionnaire
  - e) Rose Bengal staining on the ocular surface
  - f) Fluorescein staining on the ocular surface

- g) Tear film breakup time.TBUT
  - h) Intraocular pressure measuring with Goldman tonometer
  - i) Review of attachment to medication.
3. Subject's journal checking and adherence to the study
  4. Adverse events review or concomitant drug product modification
  5. Schedule the following visit

#### 11.4 *Final visit (day 90)*

1. Quality assessment questionnaire will be applied.
2. Pregnancy test performed if necessary.
3. Medical and Ophthalmic clinical history.
4. Concomitant medication evaluation.
5. OSDI questionnaire.
6. Ophthalmic Examination:

- a. Visual acuity and best-corrected visual acuity measuring
- b. OSDI questionnaire
- c. Biomicroscopy
- d. Rose Bengal staining on the ocular surface
- e. Fluorescein staining on the ocular surface
- f. Intraocular pressure measuring with Goldman tonometer
- g. Schirmer test.
- h. Drug induced mydriasis with tropicamide/phenylephrine.
- i. Fundoscopy on a slit lamp with a 90D or 78D fundus lens.
- j. Impression cytology.
- k. Ask for the return of the drug product given on the baseline visit.
- l. Schedule the safety phone call.

7. Subject's journal review and adherence to the study.

8. Adverse events review or concomitant drug product modification.

#### *11.5 Follow up phone call (day 105)*

1. Investigate about possible adverse events related with the use of the drug.

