## 6. Summary

---

Drug product ID	PRO-087
Study drug:	0.1% sodium hyaluronate, free-preservative 0.18% chondroitin sulphate
Therapeutic indication:	Ocular surface lubricant
Protocol ID:	SOPH087-0415/IV
Sponsor:	Laboratorios Sophia, S.A. de C.V.
Version:	2
Date:	February 2016
Study title	Efficacy and Safety of the Ophthalmic Solution PRO-087 versus Systane ® Ultra and Systane ® Ultra Preservative Free on the Tear Film Dysfunction Syndrome from Mild to Moderate  Clinical trial

Main objective	To evaluate the effectiveness of preservative-free ophthalmic formulation PRO-087 (by Laboratorios Sophia, S.A. de C.V.) to restore the anatomical and physiological characteristics of the ocular surface, as well as its distribution and the characteristics of the mild to moderate tear film dysfunction syndrome compared to Systane ® Ultra and Ultra Systane ® preservative free (by Laboratorios Alcon, S.A. de C.V.).
Study design	Controlled, randomized, double-blind, masked clinical study, comparing the safety and efficacy of preservative-free PRO-087 vs Systane Ultra with preservative and Systane Ultra preservative free, in subjects with mild to moderate tear film dysfunction syndrome, for a period of 90 days plus 15 days of remote surveillance, in which one of the three agents will be administered (PRO-087, Systane® Ultra or Systane® Ultra preservative free) with a q.i.d. dosage. in both eyes, with regular follow-up visits (5 overall).
Variables to evaluate	
Best-corrected visual acuity
 
Intraocular pressure
 
Ocular surface
 
Anterior segment examination
 
Posterior segment examination
 
Tear film break-up time
 
Schirmer test
 
Corneal depithelization
 
Goblet cells count
 
Adverse events

Groups	Subjects with a clinical diagnosis of mild to moderate tear film dysfunction syndrome between 18 and 90 years old, without concomitant eye diseases nor requiring different treatments of any of the three interventions in this study They will be randomized in 3 groups where PRO-087, Systane® Ultra o Systane® Ultra preservative free will be administered.

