#### 7.6 *Ethic considerations*

This protocol conforms to the Good Clinical Practices (GCP) and principles from the 18th Medical Assembly in Helsinki, Finland in 1964 and the amendments made in Tokyo, Japan 1975, Venice, Italy 1983, Hong Kong 1989 and the 48th General Assembly Somerset West, South Africa in 1996, 59th General Assembly, Seoul, Korea, 2008, 64th General Assembly, Fortaleza, Brazil, 2013, where medical research (clinical research) is contemplated.

Also, according to the specifications of the General Law of Health of Mexico, on research for health, section 17, this study is considered on the subsection III with greater risk to the minimum, by the cell sampling and drug administration. Under this legal framework, the full respect for the person, life and safety is maintained.

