### *18.1 Adverse event, definition and communication*

#### *18.1.1 General aspects*

During the study, adverse events (AE) may occur, these can be associated or not with the study drug.

If at any moment any of the study patients would have any adverse event classified as serious deriving from the administration of the drug, actions will be taken as per the guidelines of Official Mexican Standard 220 SSA1 2012 Installation and operation of Pharmacovigilance. The administration of the drug will be interrupted and the administration of an alternative therapy will be ordered, at the discretion of the principal investigator.

An adverse event is any adverse medical occurrence in a clinical research patient or subject to whom a pharmaceutical product has been administered and that does not necessarily have a causal relationship with this treatment. Therefore, an AE might be any unfavorable and non-intentional sign (including an abnormal laboratory finding), symptom or disease temporarily associated with the use of a (investigational) drug product whether it is related or not.

The investigator must report the adverse events occurred during the realization of the study from the moment a patient signs the informed consent to be included in the clinical study until the last procedure described in the approved study protocol version has ended.

In all cases, the etiology must be identified as far as possible and notify the study sponsor. An “unexpected adverse event” is any AE that is not identified in nature, seriousness or frequency in the investigator’s brochure or in the risks information described in this protocol.

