#### *18.6.1 Serious adverse events occurring after the trial*

The sponsor must be notified of all the SAEs occurring within 15 days after the last administration of the study drug or after the end of the trial for the subject.

The sponsor must also be notified of any event occurring in any moment after the end of the trial and that might be related to the study treatment in the opinion of the investigator.

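### The day-105 safety call asks only about drug-related events and is arranged only at the day-90 visit, which is narrower than the plan's own rules for reporting serious adverse events

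*Combined protocol and SAP*

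**What the plan says.** **The call.** Section 6 describes the study as running "for a period of 90 days plus 15 days of remote surveillance". Section 11.5 lists one task for the day-105 contact: "Investigate about possible adverse events related with the use of the drug". In the Section 9 schedule the safety call is marked at day 105, but the row for adverse event evaluation is marked only at days 7, 30, 60 and 90. The call is set up by an item in the final-visit list (Section 11.4, day 90): "Schedule the safety phone call".

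**The reporting rules.** Section 18.1.1 defines an adverse event without requiring a causal link and says: "The investigator must report the adverse events occurred during the realization of the study from the moment a patient signs the informed consent". That duty runs until the last procedure in the approved protocol is over. Section 18.5.6 requires all SAEs to be notified irrespective of their relationship to the drug. Section 18.6.1 adds: "The sponsor must be notified of all the SAEs occurring within 15 days after the last administration of the study drug". The same sentence offers the subject's end of trial as an alternative starting point. Section 18.6.1 also asks for any later event, at any time, that the investigator thinks may be due to treatment.

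**Procedures and leavers.** Section 7.6 classes the study as "with greater risk to the minimum, by the cell sampling and drug administration". The second cell sampling, tonometry and drug-induced mydriasis take place on day 90. Item 8 of that visit is "Adverse events review or concomitant drug product modification", listed after the procedures in item 6. For subjects who leave, Section 17.4 asks the investigator to attempt a final assessment as soon as possible.

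**The concern.** Under Section 18.5 the investigator judges causality once an event is known, and unrelated and unknown are valid answers. A caller who asks only about drug-related events applies that judgement at the question, so an event that the subject or caller does not link to the drops may never be recorded. This matters most for two groups:

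- **Completers with a delayed reaction to the day-90 procedures.** The plan itself names cell sampling as a source of risk. The first sampling is followed by a full adverse event evaluation on day 7; the second is followed only by the restricted question.
- **Subjects who stop early.** The SAE window in Section 18.6.1 is counted from the last dose or the subject's end of trial, but the call is tied to day 105 and to attending day 90. Early exit is built in: Section 12.2.3 removes subjects whose break-up time falls below 5 seconds, and Section 12.1 admits subjects just above 5 seconds. Some early leavers will have worsened, so this is not a group in which to relax safety follow-up.

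At stake is whether the post-treatment data can support a statement about events of any cause.

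**Working it through.** No power or error-rate formula applies. The check sets the texts side by side and then does the calendar arithmetic.

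**1. Scope of the question against scope of the duty**

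| Source | Which events | Period |
|---|---|---|
| 11.5 | those related to the drug | day-105 call |
| 18.1.1 | all adverse events, any cause | consent to the last protocol procedure |
| 18.5.6 | all SAEs, any cause | when they become known |
| 18.6.1 | all SAEs | 15 days after last dose or end of trial |
| 18.6.1 | any event possibly due to treatment | any time after the trial |

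The question in 11.5 is narrower than the SAE rows on any reading. It is narrower than 18.1.1 only if the call counts as the last protocol procedure, which the documents do not settle.

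**2. The plan's own timing.** 90 + 15 = 105. Day 105 reproduces as the close of the window for a subject whose last dose is on day 90.

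**3. Earlier stops.** For a last dose on day d, the window counted from that dose closes on day d + 15, and a call on day 105 would come 105 − d days after the last dose.

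| Last dose (d) | Window closes (d + 15) | Days from last dose to day 105 |
|---|---|---|
| 7 | 22 | 98 |
| 30 | 45 | 75 |
| 60 | 75 | 45 |
| 90 | 105 | 15 |

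Only the last row matches. In the others the window closes before day 105 and the plan sets no contact at its close. The final column shows what a fixed day-105 call would mean; the plan does not say that early stoppers receive one.

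**4. Order of magnitude.** Section 13.3 raises 80 per group to 96 for losses. 3 × (96 − 80) = 48, and 48 / 288 = 16.7%. This is a sample-size allowance, not a forecast of treatment stoppers.

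**The case against.** The strongest reply is that the trial proper ends on day 90. Section 7.1 gives a 90-day follow-up, and Section 18.6.1 is headed as covering events after the trial. After that point the plan wants all SAEs, plus other events that might be due to treatment, and the question in 11.5 fits that second duty. This reading is tenable, which is why the conflict with the all-cause rule in 18.1.1 is stated only conditionally. It leaves unrelated SAEs unasked, so a mismatch remains. It is also fair that the restriction is inferred from a one-item list, and that the schedule labels the contact simply as a safety call.

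Several stronger readings are tempting, but the documents do not support them:

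- **That these events are missed.** Item 8 on day 90 can catch immediate procedure effects, Section 17.4 requires an attempted contact with leavers, and Section 18.5.6 names spontaneous reports as a source of SAEs.
- **That every adverse event must be collected for 15 days after an early stop.** The explicit 15-day duty covers SAEs.
- **That 288 day-90 samplings and 48 early leavers are both affected.** These cannot both occur: if 48 leave before day 90, at most 288 − 48 = 240 are sampled then.
- **That the comparison between arms is biased.** All arms get the same question, and no differential effect is shown. The safety rule above Section 14.3.1 is framed on subjects who comply with all visits, so events after an early stop would not normally enter it.

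**Conclusion.** The point holds as a gap in active collection. The day-105 call is worded more narrowly than the SAE duties in 18.5.6 and 18.6.1. It is also narrower than the all-cause rule in 18.1.1 if the call is the last protocol procedure. For completers, unrelated events and delayed effects of the day-90 procedures are not actively asked about. For early stoppers, the final assessment under 17.4 is made as soon as possible and so cannot be relied on to span 15 days; no contact is set for the end of the window.

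The size cannot be stated as a number of events, because the documents give no event rate and no figure for treatment stoppers. The 48 of 288 is an order of magnitude for subjects who may not reach the visit where the call is arranged, and some of them may be unreachable or may refuse contact. The conclusion assumes that sites follow 11.5 as written. It is a cheap improvement to safety ascertainment and does not put the efficacy comparison in doubt.

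**What to change.** 1. **Section 11.5:** ask about all adverse events since the last contact, related or not, naming the day-90 procedures as a prompt. Causality is then assigned under Section 18.5.
2. **Timing:** define the call as 15 days after each subject's last dose, which stays day 105 for completers who dose to day 90.
3. **Section 17.4:** add the same call for withdrawn or eliminated subjects who have not refused contact, arranged when they leave.
4. **Section 18.1.1:** state whether the call is the last protocol procedure, so that the end of the adverse event window is clear.
5. **Section 9:** for consistency, mark adverse event evaluation at the call. This is tidying, since the call already has its own row.

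The cost is a few lines of wording and a small number of extra short calls, on the order of the planned losses at most if those prove accurate. The reported event count may rise slightly. Completers' calls already exist, and no treatment rule changes.
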